#### 8.1 Inclusion Criteria

Written informed consent must be obtained before any study specific assessment is performed. Upon signing informed consent, the subject is considered enrolled in the study.

Subjects eligible for inclusion in this study must fulfill all of the following criteria:

- 1. Subject must be able to understand and sign an IRB/IEC approved Informed Consent form.
- 2. Willing and able to attend all scheduled study visits as required per protocol.
- 3. Subjects must be  $\geq 38$  and  $\leq 58$  years of age.
- 4. Current contact lens wearers (during the past 3 months for a minimum of 5 days per week and 6 hours per day) of any MF contact lens (with a preference for Alcon

TDOC-0055656 Effective

Page 32 of 59

Precision Profile Design wearers) with a LO or MED ADD (or equivalent to an ADD of max +2.00 D).

OR

Current PAL wearers (wearing spectacles for a minimum of 5 days per week and 6 hours per day) with a prescription check in the last 12 months and spectacles up to date based on the prescription check with an ADD no higher than +2.00 D and a spherical refractive error between -0.50 and -6.50 D.

- 5. Contact lens wearers: manifest cylinder (at screening) less than or equal to 0.75 D in each eye and a spherical refractive error (vertex distance 10-14mm) between -0.50 and -6.50 D
- 6. Subjects' BCVA vision with manifest refraction must be 0.1 (logMAR) or better in each eye at distance at Visit 2.
- 7. Willing to discontinue artificial tears and rewetting drops within approximately 2 hours prior to or during study Visit 2.

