#### Table 9–2 **Control Product**

Control Product(s)	Progressive addition lens spectacles
Manufacturer	N/A
Indication for Use	Subjects will use their habitual progressive addition lens spectacles
	as instructed by their eye care professional.

2.0; Most-Recent; Effective; CURRENT

Page 36 of 59

Product description	Progressive addition lens spectacles
and parameters	
available for this	
study	
Formulation	N/A
Usage	N/A
Number/Amount of	N/A
Product to be	
Provided to the	
subject	
Packaging	N/A
description	
Labeling description	N/A
Storage conditions	N/A
Additional	N/A
identifying	
information	
Supply	Subject will provide their own habitual progressive addition spectacles

The study lenses must be maintained within specified environmental condition, per the labeling.

More information on the test products can be found in the Package Inserts, Directions for Use.

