## 12.4 Effectiveness Analyses

This study	defines 1 primary,			
	All effectiveness evaluations will use the FAS as the primary analysis set.			
	analyses of the primary	will be		
conducted using the PP Analysis Set only if the number of subjects excluded from the PP				
Analysis S	Set exceeds 5% of the FAS.			

A sequential gatekeeping strategy will be used to control testing of multiple effectiveness endpoints. Therefore, the overall Type I error will be maintained at one-sided 0.05 with the following testing order:

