## 12.8 Sample Size Justification

Sample size calculation is based on published results regarding response time for distance and near visual acuity, with high and low contrast.

To demonstrate noninferiority (margin = 0.5 seconds) as a one-tailed hypothesis with  $\alpha = 0.05$ , and using a common standard deviation of 0.456, 80% power can be attained with a sample size of 48 (12 per group). For a comparison using a 3:1 ratio, required sample sizes for 80% power are 24:8 (test:control).

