### 4.3 Statistical Methods for Effectiveness Analyses

#### 4.3.1 Primary Effectiveness Analyses

A mixed effect repeated measures model will be utilized to test these hypotheses, with a term for treatment (4 levels: AOHG MF, DT1 MF, DACP MF, and PAL). Within-subject correlation due to multiple observations per subject will be accounted for. Difference between MF (pooling all 3 MF groups) and PAL and the corresponding one-sided 95% upper confidence limit (UCL) will be computed. Noninferiority in transition time will be declared if the UCL is less than 0.5. Furthermore, if noninferiority is demonstrated, subsequent superiority will be tested and declared if UCL is less than 0. Otherwise, no further testing will be carried out on this endpoint.

Analysis of the mixed effect repeated measures model will be implemented in SAS. The pseudocode is provided below.

```
proc sort data = studydata;  
  by subject;  
run;
```

```
proc mixed data = studydata;  
  class subject lens;  
  model transitiontime = lens;  
  random subject;  
  repeated / subj = subject type = cs;
```

```
lsmeans lens;  
contrast 'Compare MF vs PALs' lens 1 1 1 -3;  
run;
```

Additionally, descriptive statistics will also be provided summarize:

- Average transition time for each individual MF lens group
- Average transition time for distance to intermediate viewing
- Average transition time for intermediate to distance viewing

[REDACTED]

[REDACTED]

[Redacted]

[Redacted]

[Redacted]

[Redacted]

[Redacted]

[Redacted]

[Redacted]

[Redacted]

[Redacted]

[Redacted]

[Redacted]

[Redacted]

[Redacted]

[Redacted]

[REDACTED]

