## 7 Sample Size and Power Calculations

Sample size calculation is based on published results regarding response time for distance and near visual acuity, with high and low contrast.

To demonstrate noninferiority (margin = 0.5 seconds) as a one-tailed hypothesis with  $\alpha = 0.05$ , and using a common standard deviation of 0.456, 80% power can be attained with a sample size of 48 (12 per group). For a comparison using a 3:1 ratio, required sample sizes for 80% power are 24:8 (test:control).

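### The visible primary model assumes one common variance for MF and PAL in a 36:12 comparison with a non-randomized control, so the one-sided 5% error is not protected if the variances differ

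*SAP*

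**What the plan says.** SAP 4.3.1 tests MF minus PAL in a mixed model with a four-level lens term. Its pseudocode has a random subject effect and "repeated / subj = subject type = cs". Neither statement carries a GROUP= option, and no degrees-of-freedom method is named. The three MF arms are averaged and compared with PAL. Noninferiority is declared if the one-sided 95% upper confidence limit (UCL) is below 0.5, and superiority then follows if the same limit is below 0. Protocol 12.4.1.2 describes a generalized linear model with a treatment term and is silent on variance structure.

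Protocol 12.4 promises that "the overall Type I error will be maintained at one-sided 0.05". The target is 12 completers in each of four groups, hence 36 MF and 12 PAL. Protocol 12.8 sizes the trial "using a common standard deviation of 0.456".

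On how the groups are formed:
- Protocol 9.3 randomizes only the contact lens wearers.
- For the control, Table 9–2 says "Subject will provide their own habitual progressive addition spectacles".
- Inclusion criterion 5 reads "Contact lens wearers: manifest cylinder (at screening) less than or equal to 0.75 D" for each eye. No cylinder limit is stated for PAL wearers.

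**The concern.** With 3:1 allocation, the two halves of the test depend on different subjects. The pooled variance draws 33 of its 44 degrees of freedom from the MF arms, while the true standard error of the contrast depends mainly on the 12 PAL subjects. If PAL transition times vary more than MF times, the pooled standard error is too small, the UCL is too low, and both claims are made too easily. If PAL times vary less, the UCL is needlessly high.

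Equal spread cannot be taken for granted, because randomization does not link the two groups. The MF arms share an optical design and fitting process (Protocol 5.1), have capped cylinder, and lose subjects in whom no successful fit is achieved (Protocol 10). PAL wearers bring spectacles of unspecified make. The common SD is a planning assumption taken from published response times for distance and near acuity; it is not evidence on the spread of transition times in these two groups.

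**Working it through.** **Inputs.** From the documents: margin 0.5 s, one-sided α 0.05, common SD 0.456, planned 36:12. Assumed: true difference 0 for power (not stated, but it reproduces the plan's sizes), and a PAL:MF SD ratio r between 0.5 and 2 (the documents give none).

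**Step 1: the plan's own figures.** The standard error (SE) is 0.456 × √(1/n₁ + 1/n₀). Power comes from the noncentral t distribution with noncentrality 0.5/SE.
- 24:8 gives SE 0.186, noncentrality 2.686 and power 83.6%; 21:7 gives 78.9%.
- 12:12 gives the same SE and power 83.1%; 11:11 gives 79.9%.
- So the stated 24:8 and 12 per group are the smallest sizes that reach 80%.
- 36:12 gives SE = 0.456 × √(1/36 + 1/12) = 0.152, noncentrality 3.289 and power 94.4% on 44 degrees of freedom.

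**Step 2: approximate error of the common-variance contrast.** In units of the MF variance:
- expected pooled variance: s² = (33 + 11r²)/44
- variance the model assigns to the contrast: s² × (1/36 + 1/12) = s²/9
- true variance of the contrast: 1/36 + r²/12
- one-sided error ≈ 1 − Φ(1.645 × √[(s²/9) / (1/36 + r²/12)])

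At r = 1.5, s² = (33 + 24.75)/44 = 1.3125. The model variance is 0.1458 and the true variance is 0.0278 + 0.1875 = 0.2153. Then √(0.1458/0.2153) = 0.823, 1.645 × 0.823 = 1.354, and the error is 8.8%.

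**Step 3: simulation.** Normal subject averages were simulated for three MF groups of 12 and one PAL group of 12, with MF SD 0.456. The common-variance contrast (44 df) was compared with a contrast using a separate PAL variance and Satterthwaite df. With equal numbers of readings per subject, the contrast on subject averages equals the fixed-effect contrast from the common compound-symmetry model.

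| r | Error, approximation | Error, common variance | Error, separate variances | Power, common | Power, separate |
|---|---|---|---|---|---|
| 0.5 | 1.2% | 1.4% | 5.0% | 99.5% | 99.9% |
| 0.67 | 2.3% | 2.4% | 5.0% | 98.7% | 99.5% |
| 0.8 | 3.3% | 3.4% | 5.0% | 97.4% | 98.1% |
| 1 | 5.0% | 5.0% | 5.0% | 94.4% | 93.6% |
| 1.25 | 7.0% | 7.0% | 5.1% | 89.3% | 83.9% |
| 1.5 | 8.8% | 8.7% | 5.0% | 83.7% | 72.7% |
| 2 | 11.4% | 11.4% | 5.1% | 72.5% | 53.5% |

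Error is at a true difference of 0.5 and power is for noninferiority at a true difference of 0. The superiority error at a true difference of 0 agrees with the error columns within simulation error, as it must, because it uses the same limit.

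**Step 4: in seconds.** At r = 1.5 the common-variance half-width is about 1.680 × 0.152 × √1.3125 = 0.29 s. The separate-variance half-width is 1.758 × 0.456 × √0.2153 = 0.37 s on about 14.4 df. The limit sits about 0.08 s too low, or 16% of the margin.

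**The case against.** The strongest reply is that nothing in the documents says the variances differ. The only variance figure is one common SD, and under it the planned test is exact. A ratio of 2 means a PAL SD of 0.912 and a fourfold variance, which no passage supports. This stands: every figure away from 5% is conditional.

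A reader might also infer that PAL, with its mixed products, must be the more variable arm. The documents do not support that. PAL spectacles must be current with a prescription check in the last 12 months, with ADD up to +2.00 D and the same sphere range as the contact lens wearers. The acuity requirement applies to everyone. PAL subjects use the correction they wear at least 5 days a week. The MF side pools three materials, worn for about 2 to 3 hours by habitual wearers of any MF lens, and fitting may follow the guide or the investigator's discretion. Table 9-1 lists no cylinder power for the study lenses, so up to 0.75 D may go uncorrected. PAL could be the less variable arm, and the planned test would then be conservative.

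Three further points stand in part:
- Much of the SAP after the primary pseudocode is redacted, so the absence of a sensitivity analysis cannot be asserted. That would not change the visible primary model.
- SAP section 4 allows alternative models and gives non-convergence only as an example. It does not commit to anything for unequal variances.
- The listing is pseudocode and may be incomplete. The reasonable response is to complete it before the data are seen, since a variance model chosen afterwards could be chosen for its result.

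**Conclusion.** The point holds as a conditional one. The visible primary analysis has no protection against unequal variances at 36:12, with a control group that randomization does not make comparable. If the PAL SD were 1.25 to 2 times the MF SD, the promised one-sided 5% would become about 7% to 11%, for noninferiority and superiority alike. If it were 0.67 or 0.5 times the MF SD, the error would be about 2.4% or 1.4%. At equal SDs it is 5.0%.

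A reader might go further and conclude that the plan fails to control its error rate. The documents do not support that, because they give neither the ratio nor its direction. The figures assume normal subject averages, equal numbers of readings per subject and 12 completers per group. This is a worthwhile, inexpensive improvement and not a demonstrated failure.

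**What to change.** State in SAP 4.3.1 that the primary MF minus PAL UCL comes from a model with separate MF and PAL variances and Satterthwaite or Kenward-Roger degrees of freedom. Either form works, using a two-level MF-or-PAL indicator:
- **Subject averages:** remove `random subject`, which cannot be separated from the residual with one record per subject, and use `REPEATED / GROUP=` the indicator.
- **Individual readings:** let both the between-subject and the within-subject variance differ by the indicator. One way is to keep compound symmetry with `GROUP=` on the REPEATED statement and drop the random subject effect, which otherwise models the same within-subject correlation a second time.

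Add `DDFM=SATTERTHWAITE` or `DDFM=KR` to the MODEL statement. Obtain the limit from an ESTIMATE statement with the MF coefficients divided by 3, because the listed CONTRAST statement gives a test and no confidence limit.

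The cost is a few lines of code, an indicator variable and a sentence or two in the SAP. If the SDs are equal, power falls by about 1 point (93.6% versus 94.4%), still well above the planned 80%. If PAL is more variable, power is lower, about 73% at a ratio of 1.5. The common-variance model's 84% in that setting is reached only by running at about 9% error. If PAL is less variable, the change gains a little power.

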#### 4.6 Interim Analysis for Effectiveness

No interim analysis is planned for the effectiveness endpoints.

### 5 Safety Analysis Strategy

#### 5.1 Safety Endpoints

The safety endpoints are:

- Adverse events (AE)
- Biomicroscopy findings
  - Limbal hyperemia
  - Bulbar hyperemia
  - Corneal staining
  - Conjunctival staining
  - Palpebral conjunctival observations
  - Corneal epithelial edema
  - Corneal stromal edema
  - Corneal vascularization
  - Conjunctival compression/indentation
  - Chemosis

- Corneal infiltrates
  - Other findings
- Device deficiencies

## 5.2 Safety Hypotheses

There are no formal safety hypotheses in this study. The focus of the safety analysis will be a comprehensive descriptive assessment of safety endpoints listed in Section 5.1.

## 5.3 Statistical Methods for Safety Analyses

The analysis set for all safety analyses is defined in Section 2.1. Baseline will be defined as the last measurement prior to exposure to study products on Visit 2. Safety variables will be summarized descriptively.

### 5.3.1 Adverse Events

The applicable definition of an AE is in the study protocol. All AEs occurring from when a subject signs informed consent to when a subject exits the study will be accounted for in the reporting.

Analysis and presentation of pre-treatment AEs will be separated from treatment-emergent AEs occurring during the study periods. A pre-treatment AE is an event that occurs after signing informed consent but prior to exposure to study products. The period for treatment-emergent AE analysis starts from exposure to study products until the subject completes or is discontinued from the study.

The following tables and supportive listings will be provided:

- Incidence of All Ocular Treatment-Emergent Adverse Device Effects
- Incidence of All Ocular Treatment-Emergent Adverse Events, Not Related
- Incidence of All Ocular Treatment-Emergent Adverse Events, Overall
- Incidence of Ocular Serious Treatment-Emergent Adverse Device Effects
- Incidence of Ocular Serious Treatment-Emergent Adverse Events, Not Related
- Incidence of Ocular Serious Treatment-Emergent Adverse Events, Overall
- Incidence of Ocular Significant Nonserious Treatment-Emergent Adverse Device Effects

- Incidence of Ocular Significant Nonserious Treatment-Emergent Adverse Events, Not Related
- Incidence of Ocular Significant Nonserious Treatment-Emergent Adverse Events, Overall
- Incidence of All Nonocular Treatment-Emergent Adverse Device Effects
- Incidence of All Nonocular Treatment-Emergent Adverse Events, Not Related
- Incidence of All Nonocular Treatment-Emergent Adverse Events, Overall
- Incidence of Nonocular Serious Treatment-Emergent Adverse Device Effects
- Incidence of Nonocular Serious Treatment-Emergent Adverse Events, Not Related
- Incidence of Nonocular Serious Treatment-Emergent Adverse Events, Overall
- Listing of All Ocular Treatment-Emergent Adverse Events
- Listing of All Nonocular Treatment-Emergent Adverse Events
- Listing of All Ocular Pre-Treatment Adverse Events
- Listing of All Nonocular Pre-Treatment Adverse Events

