Investigational Product  Malfunction	Is defined as a preventative (vaccine), a therapeutic (drug or biologic), device, diagnostic, or palliative used as a test or control product in a clinical trial, including a product with a marketing authorization when used or assembled (formulated or packaged) in a way different from the authorized form, or when used for an unauthorized indication, or when used to gain further information about the authorized form.  Failure of a medical device to meet its performance
TVILLITATION OF	specifications or otherwise perform as intended. Performance specifications include all claims made in the labeling of the device. The intended performance of the device refers to the intended use for which the device is labeled or marketed.
Non-serious Adverse Event	Adverse event that does not meet the criteria for a serious adverse event.
Postmarketing/Post- authorization study	Any study conducted within the conditions laid down in product labelling and other conditions laid down for the marketing of the product or under normal conditions of use. A postmarketing study falls either within the definitions of an interventional or a non- interventional study and may also fall within the definition of a post-approval study.
Product Complaints	Any oral, electronic, or written communication that alleges deficiencies related to the identity (labeling), quality, durability, reliability, safety, effectiveness, or performance of a marketed product, including failure of the product, labeling or packaging to meet specifications, whether or not the product is related to or caused the alleged deficiency. A complaint may allege that an adverse event or medical device malfunction has occurred.
Randomized Subjects	Any subject who is assigned a randomized treatment.
Serious Adverse Device Effect (SADE)	Adverse device effect that has resulted in any of the consequences characteristic of a serious adverse event.
Serious Adverse Event (SAE)	
 
Adverse event that led to any of the following:
 
Death.
 
A serious deterioration in the health of the subject that either resulted in:
 

TDOC-0055656

Effective

2.0; Most-Recent; Effective; CURRENT

Page **9** of **59** 

	a. a life-threatening illness or injury.  Note: Life-threatening means that the individual was at immediate risk of death from the event as it occurred, ie, it does not include an event which hypothetically might have caused death had it occurred in a more severe form.

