Procedure/Assessment	Day 1 (May be performed same day as Visit 2)	Exposure/Exit  0-14 Days from Visit 1	Exposure/Exit  0-14 Days from  Visit 1	Visit
Informed Consent	✓			
Demographics	✓			
Medical History	✓	✓	✓	✓
Concomitant Medications	✓	✓	√	√
Inclusion/Exclusion	✓	✓	√	
Randomize		✓		
Habitual correction (type/brand, power)		√	✓	
Dispense study contact lenses in a masked manner		✓		

TDOC-0055656 Effective

Page 19 of 59

	ALL SUBJECTS	MULTIFOCAL CONTACT LENS WEARERS	PROGRESSIVE ADDITION LENS SPECTACLE WEARERS	ALL SUBJECTS
Visit	Visit 1/ Screening	Visit 2/ Exposure/Exit	Visit 2/ Exposure/Exit	Unscheduled Visit
Procedure/Assessment	Day 1 (May be performed same day as Visit 2)	0-14 Days from Visit 1	0-14 Days from Visit 1	
		✓		
Transition time during alternate distance (4 m) and intermediate (80 cm) viewing		√	√	

TDOC-0055656 2.0; Most-Recent; Effective; CURRENT Effective

Page 20 of 59

	ALL SUBJECTS	MULTIFOCAL CONTACT LENS WEARERS	PROGRESSIVE ADDITION LENS SPECTACLE WEARERS	ALL SUBJECTS
Visit	Visit 1/	Visit 2/	Visit 2/	Unscheduled
VISIT	Screening	Exposure/Exit	Exposure/Exit	Visit
Procedure/Assessment	Day 1 (May be performed same day as Visit 2)	0-14 Days from Visit 1	0-14 Days from Visit 1	
AEs	✓	√	√	✓
Device deficiencies	✓	✓		(✓)
Exit form†	(✓)	√	✓	(✓)

(✓) assessment performed as necessary, eg, decrease of VA by 2 lines or more with investigational product (IP) \*source only; † must be performed as a screening assessment and prior to study exit

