## 1.2 Study Description

Key components of the study are summarized in Table 1-1.

[figure not shown]
Table 1-1 Study Description Summary

Study Design	Prospective, randomized, parallel group, double-masked for contact lens wearers, single-masked (investigator to type of brand) for PALs wearers
Study Population	Presbyopic subjects aged $\geq 38$ and $\leq 58$ years with normal eyes (other than correction for refractive error), whose habitual correction is either any MF contact lens (with a preference for Alcon Precision Profile Design wearers) with a LO or MED ADD (or equivalent to an ADD of max +2.00 D) or progressive addition lens spectacles. Wear of habitual correction must be at least 5 days per week and at least 6 hours per day.  Target to complete: 48 (12 per group) Planned to enroll: ~60
Number of Sites	2 (1 UK, 1 US)
Test Product(s)	
 
• AIR OPTIX® plus HydraGlyde® (Iotrafilcon B) Multifocal contact lens (AOHG MF)
 
• DAILIES TOTAL1® (delefilcon A) Multifocal contact lens
 

	(DT1 MF) 
 
DAILIES® AquaComfort Plus® (nelfilcon A) Multifocal contact lens (DACP MF)
 

Control Product(s)	Progressive addition lens spectacles (PALs)
Duration of Treatment	Test product(s): Up to 3 hours Control product(s): Up to 3 hours
Visits	Visit 1 – Screening Visit 2 – Exposure/Exit [0 - 14 days from Visit 1] *  *Randomization for subjects in the contact lens group will occur at Visit 2

A study design schematic is depicted in Figure 1-1.

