**Figure Error! No text of specified style in document.–1 Study Design**

### 1.3 Randomization

A member of the Randomization Programming group at Alcon who is not part of the study team will generate the randomized allocation schedule(s) for study lens assignment.

Randomization will be implemented in Medidata Rave RTSM.

Qualifying subjects in the contact lens group will be randomized in a 1:1:1 ratio to one of 3 parallel groups to receive either AOHG MF, DT1 MF, or DACP MF, respectively. Habitual PALs wearing subjects will not be randomized.

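### Does leaving the start of exposure unnamed, for PAL wearers and during lens fitting, distort the adverse event tables?

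*SAP*

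**What the plan says.** SAP 5.3.1 splits AEs into two classes. The earlier class is defined as follows: "A pre-treatment AE is an event that occurs after signing informed consent but prior to exposure to study products". The later class is defined by its window: "The period for treatment-emergent AE analysis starts from exposure to study products until the subject completes or is discontinued from the study". Pre-treatment events are listed; treatment-emergent events go into incidence tables and listings.

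Three other parts of the SAP bear on when exposure starts.

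- **SAP 1.2, Table 1-1.** The planned duration for the control arm is "Control product(s): Up to 3 hours", the same as for the test lenses. Visit 2 is named the exposure and exit visit.
- **SAP 5.3.** The safety baseline is the last measurement before exposure, tied to Visit 2, with no restriction to one group. The section sends all safety analyses to the set defined in SAP 2.1.
- **SAP 2.1 (and Protocol 12.2.1).** Lenses used only for fitting and parameter optimization do not count as exposure for membership of the safety set. The next paragraph of SAP 2.1 puts events before first exposure into listings.

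On the PAL group, Protocol 8.1 admits "Current PAL wearers (wearing spectacles for a minimum of 5 days per week and 6 hours per day", Protocol Table 9–2 says "Subject will provide their own habitual progressive addition spectacles", and SAP 1.3 says "Habitual PALs wearing subjects will not be randomized".

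**The concern.** A treatment-emergent rule needs a start that can be programmed, and for PAL wearers none is visible. The Protocol glossary counts as investigational product anything "used as a test or control product in a clinical trial", so the habitual spectacles qualify. The subjects already wear them, bring their own pair and are not randomised. The only dispensing row visible in Protocol Table 3–1, "Dispense study contact lenses in a masked manner", is marked for contact lens wearers alone. Read in isolation, SAP 5.3.1 would put the start of PAL exposure before consent. No PAL event could then be pre-treatment, and anything in the 0 to 14 days between visits would be tabulated. The same interval would be pre-treatment for MF subjects.

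The second worry concerns MF subjects who are fitted successfully. SAP 5.3.1 does not repeat the exception for fitting lenses. An event caused by a fitting lens could therefore be tabulated (if the first lens starts exposure) or only listed (if the final pair does).

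Third, Protocol 12.6 counts two-grade biomicroscopy increases over later visits within a period. This is a parallel-group study with exposure and exit at one visit, so it has no periods and possibly no later scheduled visit.

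At stake would be a safety table whose columns cover unequal time. The first two ambiguities could both flatter the test lenses: extra time can only add PAL events, and a later start can only hold or lower MF counts.

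**Working it through.** **1. The plan's own windows.** Table 1-1 gives up to 3 hours for test and up to 3 hours for control, a ratio of 3/3 = 1.

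**2. The literal reading.** PAL window = 24 × (days between visits) + 3 hours, compared with 3 hours for MF.

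| Gap between visits | PAL window | Ratio to 3 h |
|---|---|---|
| 0 days (same day, which is allowed) | 3 h | 1 |
| 7 days | 171 h | 57 |
| 14 days (maximum) | 339 h | 113 |

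The documents give no AE rate. Assume a background of 0.05 to 0.20 events per person-month of 30.4 days. Over 14 days plus 3 hours (14.125 days), 12 PAL subjects would be expected to have 12 × 0.05 × 14.125 / 30.4 = 0.28 to 12 × 0.20 × 14.125 / 30.4 = 1.12 events. Over 3 hours (0.125 days) the same subjects would have 0.0025 to 0.0099. So the literal reading would matter if it were the plan.

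**3. Whether the literal reading can be the plan.** It fails on two counts.

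- It contradicts Table 1-1, which limits control exposure to 3 hours.
- It leaves PAL subjects without a baseline. If exposure predates consent, no study measurement precedes it, and the baseline in SAP 5.3 cannot exist for them. Whether Visit 2 in that sentence qualifies the measurement or the exposure, exposure cannot begin before Visit 2.

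SAP 5.3.1 is a subsection of 5.3 and is read with it. With a Visit 2 start in both groups the ratio returns to 1, and events between visits are pre-treatment in both.

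**4. Fitting lenses.** SAP 5.3 refers safety analyses to SAP 2.1. That section excludes fitting lenses from exposure and then speaks of first exposure. Read in sequence, this makes the final pair the start. Protocol 11.3 also removes temporary lens awareness and visual changes during fitting from AE status when the investigator judges that they can resolve within the adaptation period. That takes out the complaints most likely to arise at this stage.

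**5. Biomicroscopy.** SAP 5.3.2 plans the two-grade table without the wording about periods. Protocol 10.2.5 requires a slit-lamp examination of both eyes before exit, so a post-exposure assessment exists for each subject who completes. The Protocol phrase reads as carry-over from a multi-period template.

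**6. Size of what is left.** The planned completers are 48, or 12 per group (36 MF, 12 PAL). Moving one affected subject between table and listing changes:

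- one group by 1/12 = 8.3 points;
- the pooled MF column by 1/36 = 2.8 points;
- for one eye in a group of 24 eyes, a biomicroscopy entry by 1/24 = 4.2 points.

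These are the effects of any single event in groups this small. They do not measure a bias.

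**The case for a change.** The best case for a change is that context narrows the start to Visit 2 but still names no moment within that visit for PAL wearers. Someone must choose it, and the choice is better made before unmasking. The glossary also makes an event related to the control product an adverse device effect. Protocol 11.3 treats events on habitual MF lenses as spontaneous reports on non-study products, but it has no matching rule for habitual spectacles. Finally, the anchor goes by several names across SAP 5.3.1 and Protocol 12.6, and some of them cannot apply to a spectacle wearer.

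Much of this is accurate, but it carries little weight. PAL wearers keep the same spectacles on during Visit 2, so the exact minute at which exposure is deemed to start can affect only events within a visit of about 3 hours. The SAP's schedule (Table 10-1) has blacked-out rows marked for PAL wearers at Visit 2, and Protocol 10.2 leaves procedural detail to the manual of procedures. A time point may already be set there, and its absence from the public text cannot be counted as an omission. Under a Visit 2 start, a spectacle-related event between visits is pre-treatment and appears in the listing. The device-deficiency wording in Protocol 12.6 is rightly specific to contact lenses, because SAP 5.3.3 confines those outputs to the contact lens group. What stands is that SAP 5.3.1 could have repeated the Visit 2 anchor and the fitting-lens exception, and did not.

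**Conclusion.** No change follows. SAP 5.3.1 leaves a term short of detail, but Table 1-1, SAP 2.1 and SAP 5.3 supply the rest: exposure starts at Visit 2 in both groups, with the final pair for MF subjects. On that reading both windows are up to 3 hours. The 14-day window and the 113-fold ratio come from reading one sentence alone and are not features of the plan. An analyst with the whole SAP would reach the same convention.

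The residual effect is whether a rare Visit 2 event is tabulated or listed: 8.3 points per event in a group of 12, or 2.8 points over the 36 MF subjects. No safety hypothesis is tested, every AE from consent to exit is reported in one place or the other, and the primary comparison of transition time does not depend on the split. The biomicroscopy phrase in Protocol 12.6 is a clerical leftover that the SAP does not carry forward.

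This conclusion assumes that the SAP sections are read together, that the planned 12 completers per group are the denominators, and that the redacted schedule rows and the manual of procedures contain nothing to the contrary.
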